PTT	Partial Thromboplastin Time
SAE	Serious Adverse Event
SADR	Serious Adverse Drug Reaction
SAS	Safety Analysis Set
SDS	Standard Deviation score
SMR	Service Medical Rendu
TSH	Thyroid-Stimulating Hormone
ULIS	Units localized for school inclusion

2 Responsible parties

In this document physician refers to the individual overall responsible for the conduct of the Non-Interventional Study (NIS) at a study site.

3 Abstract

- **Title:** French registry of children treated with Norditropin[®] for short stature due to Noonan Syndrome-NS (PASS)

Planned milestones:

Milestone	Planned date
Start of data collection (FPFV)	March 2022
Last Patient First Visit (LPFV)	March 2024
Last Patient Last Visit (LPLV)	March 2028
Study progress reports	Monthly update during implementation, inclusion & follow-up
Interim report of study results	October 2025
Final report	August 2028

Background and Rationale:

Norditropin[®] (NN-220; somatropin; Novo Nordisk A/S, Denmark), a recombinant human growth therapy (rhGH) produced by genetic recombinant technology, is currently the sole approved medication for the treatment of short stature due to NS in France. In October 2020, the Transparency Committee (CT- *Commission de Transparence*) rated the actual clinical benefit (SMR- *Service Medical Rendu*) of Norditropin[®] as “important” and issued a favourable opinion for inclusion of Norditropin[®] on the list of reimbursed proprietary medicinal products in NS children with short stature (< -2 SDS)(1).

Despite the existing literature documenting the effect of GH therapy on height outcomes, long-term effectiveness and safety data associated with Norditropin[®] treatment is needed. Furthermore, information on quality of life in NS patients remains scarce. Hence, the CT has requested the development of a national registry of NS children with short stature and treated with Norditropin[®] until adulthood. Data should be available within five years. This registry shall provide information on long-term clinical evolution of these patients (e.g adult height and quality of life) and on the safety profile of Norditropin[®] (notably the risk of tumour, effect on glucose metabolism and cardiac defects). The CT has also recommended that data collection be defined in collaboration with French reference and competence centres.

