8.1 Study design

This study is a PASS. This is a non-interventional registry of children treated with Norditropin® for short stature due to NS. This study aims to provide data on long-term growth evolution and safety of Norditropin® as well as HRQoL data. This registry will include the entirety of children treated with Norditropin® for short stature due to NS over the inclusion period. In consequence, this registry will enroll both patients who received Norditropin® before its marketing authorization for short stature due to NS in France and patients who received Norditropin® after its approval.

This study presents both a prospective and retrospective design. Data will be collected for 3 groups of patients:

- Incident patients: Children initiating Norditropin® upon their inclusion in the study.
- Prevalent patients:
 - Children who were already treated with Norditropin® before their inclusion in the study and finished their growth upon their inclusion. For these patients, all data will be collected retrospectively from medical records.
 - Children who were already treated with Norditropin® before their inclusion in the study and who did not finish their growth upon their inclusion. For these patients, data will be collected both retrospectively and prospectively.

HRQoL data will be collected on incident patients only.

The inclusion period will last for 24 months and patients will be followed-up for 4 years with possibility of extension for patients who did not reach AH. This will allow to provide interim results on October 2025 to the HAS.

All information will be collected as per physicians' routine of care and as this study is non-interventional, neither clinical interventions nor laboratory assessments will be imposed as per this protocol.

* The follow-up period in this study is 4 years with possibility of extension for patients who did not reach adult height.

[figure not shown]

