8.1.1.1 Primary endpoint

Table 2 Primary endpoint

Title of endpoint	Time frame	Unit
Change in height standard deviation score	From start of Norditropin® treatment until end of follow-up	SDS

The change in height in SDS (measured in scores -10 to +10) will be derived from recent national growth chart reference(2).

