8.1.1.2 Secondary endpoints

Secondary objective-1: To evaluate the long-term safety profile of Norditropin®.

All drug related adverse reactions (ADR), serious adverse drug reactions (SADR), serious adverse events (SAE) and adverse events (AE) will be recorded and described up to the end of growth development or end of follow-up if earlier. The endpoints related to the secondary objective-1 are listed in [Table 3](#).

Table 3 Secondary endpoints in relation to secondary objective 1

Title of endpoint	Time frame	Unit
Number of adverse drug reactions (ADR)	From start of Norditropin® until end of follow-up	Count of events
Number of serious adverse drug reactions (SADR),	From start of Norditropin® until end of follow-up	Count of events
Number of serious adverse events (SAE)	From start of Norditropin® until end of follow-up	Count of events
Number of adverse events (AE)	From start of Norditropin® until end of follow-up	Count of events

Secondary objective-2: To describe the socio-demographic and clinical characteristics of patients. The endpoints related to the secondary objective-2 are listed in [Table 4](#).

Table 4 Secondary endpoints in relation to secondary objective 2

Title of endpoint	Time frame	Unit
Socio-demographic		
Education	From start of Norditropin® treatment until end of follow-up	NA
School level	From start of Norditropin® treatment until end of follow-up	NA
Educational measures	From start of Norditropin® treatment until end of follow-up	NA
Clinical characteristics		

Title of endpoint	Time frame	Unit
Tanner stage	At all visits	NA
Change in pulse rate	From start of Norditropin® treatment until end of follow-up	Beats per minute
Change in diastolic blood pressure	From start of Norditropin® treatment until end of follow-up	mm Hg
Change in systolic blood pressure	From start of Norditropin® treatment until end of follow-up	mm Hg
Change in corrected QT-interval (Electrocardiogram)	From start of Norditropin® treatment until end of follow-up	msec
Change in echocardiogram parameters	From start of Norditropin® treatment until end of follow-up	mm (Left ventricular interventricular septal maximum thickness in diastole) mm (Left ventricular end diastolic diameter) % (Left Ventricular Fractional Shortening (LVFS)) % (Left Ventricular Ejection Fraction (LVEF)) Cm/s (Diastolic function (Ea)) Cm/s (Diastolic function (Aa))

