Number of modifications (change in dosage/ temporary stop)	From start of Norditropin® treatment until end of follow-up	Count of events
Reasons for treatment modifications	From start of Norditropin® treatment until end of follow-up	NA
Duration of temporary stop	From start of Norditropin® treatment until end of follow-up	Months

Title of endpoint	Time frame	Unit
Total duration of Norditropin [®] treatment	From start of Norditropin [®] treatment until end of follow-up	Years
Total cumulative dose of Norditropin [®] treatment	From start of Norditropin [®] treatment until end of follow-up	mg/kg
Other NS treatments		
Type and number of concomitant treatments	At all visits	Count of events
Type and number of concomitant treatments linked to an adverse event	At all visits	Count of events

Secondary objective-4: To describe the NS in terms of auxological characteristics, diagnosis and NS comorbidities.

The endpoints related to the secondary objective-4 are listed in [Table 6](#).

Table 6 Secondary endpoints in relation to secondary objective 4

Title of endpoint	Time frame	Unit
Auxological characteristics		
Change in weight	From start of Norditropin [®] treatment until end of follow-up	SDS
Change in body mass index (BMI)	From start of Norditropin [®] treatment until end of follow-up	Kg/m ²
Change in bone age	From start of Norditropin [®] treatment until end of follow-up	year
Change in height velocity	From start of Norditropin [®] treatment until end of follow-up	cm/year and SDS/year
Type and number of NS comorbidities	At all visits	NA

Secondary objective-5: To evaluate the evolution of Health-Related Quality of Life (HRQoL) of patients/Legally Acceptable Representative (LAR).

The endpoints related to the secondary objective-5 are listed in [Table 7](#).

Table 7 Secondary endpoint in relation to secondary objective 5

Title of endpoint	Time frame	Unit
Change in HRQoL score (PedsQL)	From start of Norditropin [®] treatment until end of follow-up	NA

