8.3 Variables

Table 10 Variables

Variables	Operational Definition	Measurement
Socio-demographic		
Education	Categorical variable : 
 • Standard education • Education with assistance (special needs assistant, units localized for school inclusion (ULIS classes) and medical and education institute) • Educational measures (physiotherapy, psychomotricity, occupational therapy and speech therapy) 	Endpoints
School (education) level	Categorical variable : 
 • Preschool • Elementary school • Secondary school • High school 	Endpoints
Educational measures	Categorical variable : 
 • Physiotherapy • Psychomotricity • Occupational therapy • Speech therapy 	Endpoints
Age of puberty	Continuous variable	Endpoints
Age of onset of menstruations (female only)	Continuous variable	Endpoints
Tanner stage	3 sub-scales : Pubic hair scale (both females and males) Female breast development scale (for females only) Male external genitalia scale (male only) Categorical variable : 
 • Stage 1 • Stage 2 • Stage 3 • Stage 4 • Stage 5 	Endpoints
Clinical		
Comorbidities of interest not related to NS	Categorical variable	Endpoints
Pulse rate	Continuous variable	Endpoints
Diastolic pressure	Continuous variable	Endpoints
Systolic pressure	Continuous variable	Endpoints

Variables	Operational Definition	Measurement
Echocardiogram (left ventricular interventricular septal maximum thickness in diastole, left ventricular end diastolic diameter, LVFS, LVEF and diastolic function (Ea and Aa))	Continuous variable	Endpoints
corrected QT interval	Continuous variable	Endpoints
Complete blood count (CBC) (Hb, white blood cells, lymphocytes, monocytes and platelets)	Continuous variable	Endpoints
IGF-1 level	Continuous variable	Endpoints
IGFBP- 3 level	Continuous variable	Continuous variable
TSH	Continuous variable	Continuous variable
FT4	Continuous variable	Continuous variable
HbA _{1c} level	Continuous variable	Endpoints
Fasting insulin blood level	Continuous variable	Endpoints
Fasting glucose blood level	Continuous variable	Endpoints
Fasting total cholesterol	Continuous variable	Endpoints
Fasting triglycerides	Continuous variable	Endpoints
Fasting HDL level	Continuous variable	Endpoints
Fasting LDL level	Continuous variable	Endpoints
Fasting ratio total cholesterol/ HDL level	Continuous variable	Endpoints
Inhibin-B	Continuous variable	Endpoints

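### Septal thickness and left ventricular diameter are endpoints in raw mm only, so ordinary growth cannot be told apart from a cardiac effect

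*Protocol*

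**What the plan says.** The echocardiogram row of Table 4 (Section 8.1.1.2) lists six parameters. Two are lengths: "mm (Left ventricular interventricular septal maximum thickness in diastole) mm (Left ventricular end diastolic diameter". The other four are not: "Left Ventricular Fractional Shortening (LVFS)) % (Left Ventricular Ejection Fraction (LVEF" are percentages, and the diastolic velocities Ea and Aa are in cm/s. Change is counted from treatment start to the end of follow-up.

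Table 10 (Section 8.3) repeats the list, "left ventricular interventricular septal maximum thickness in diastole, left ventricular end diastolic diameter, LVFS, LVEF and diastolic function (Ea and Aa", and classes all six simply as continuous.

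In Table 6, "Change in body mass index (BMI" (the row ends with a closing bracket) is in kg/m². The row directly above it, "Change in weight", is in SDS.

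Elsewhere the protocol does standardise. The primary endpoint is "Change in height standard deviation score", taken from a national growth reference. IGF-1 is given in ng/ml and SDS, and height velocity in cm/year and SDS/year.

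Section 8.1 describes the design: "This is a non-interventional registry of children treated with Norditropin® for short stature due to NS". Section 8.2.6 sets no limit on age or bone age. Secondary endpoints are only described (Section 8.7.2.2), overall and by subgroup, and treatment duration is one of the subgroups (Section 8.7.1). The only planned adjustment of descriptive results is weighting by centre and patient (Section 8.7.2).

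**The concern.** Heart dimensions increase as a child grows. A change in mm over several years of childhood therefore contains growth as well as any effect of disease or treatment, and no comparator is available to subtract the growth. Sampling weights do not remove it.

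The windows also differ widely. Incident patients contribute 4 years, extendable. Section 8.5 counts prevalent patients who started treatment from 2010, and their change also runs from treatment start. Inclusion opens in 2022, so some windows can approach or exceed a decade. A pooled mean in mm then depends on the mix of ages and durations.

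The treatment-duration subgroup sharpens the problem. Children treated longer have usually also grown for longer, so the mm change rises across the groups mechanically and can resemble an exposure-response pattern. Section 8.7.2 allows exploratory two-sided 5% tests between subgroups, so the artefact could be reported as significant.

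The subject is not incidental. According to the Abstract, the Transparency Committee wanted information "on the safety profile of Norditropin[®] (notably the risk of tumour, effect on glucose metabolism and cardiac defects" among other things, and hypertrophic cardiomyopathy is a listed Noonan comorbidity in Table 10.

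**Working it through.** The protocol states no figure for heart dimensions or BMI, so there is nothing of its own to reproduce on this point. The precision figures in Table 11 concern height and play no part here.

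**Inputs.** From the protocol: the units, the 4-year extendable follow-up, the absence of an age limit, and the expected 4-year height gain of 1.14 SDS (Section 8.5). Assumed for illustration: start height 95 to 110 cm, growth 4 to 8 cm/year, a heart that stays in proportion to the child, and a linear dimension proportional to height^b with b from 0.5 to 1.0.

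**1. Growth alone over 4 years.** Relative change = (H1/H0)^b − 1.
- Lowest: 110 cm at 4 cm/year gives 126 cm; (126/110)^0.5 − 1 = 7.0%.
- Highest: 95 cm at 8 cm/year gives 127 cm; (127/95)^1.0 − 1 = 33.7%.

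With an assumed 6 mm septum this is +0.4 to +2.0 mm. With an assumed 32 mm diameter it is +2.2 to +10.8 mm. None of it is a cardiac effect.

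**2. Cross-check by body surface area.** Take BSA = √(height × weight / 3600), with dimensions proportional to √BSA. A child going from 100 cm and 15 kg to 125 cm and 25 kg moves from 0.645 to 0.932 m², a ratio of 1.44, and √1.44 = 1.20. The 20% rise lies inside the range in step 1.

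**3. Effect of duration.** Start at 95 cm, grow 6 cm/year, b = 0.75.
- 4 years: (119/95)^0.75 − 1 = 18.4%.
- 8 years: (143/95)^0.75 − 1 = 35.9%.

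Doubling the window roughly doubles the apparent change in a child whose heart has kept its proportion. Over the whole assumed range, 8 years gives 13.6% to 67.4%.

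**4. Share due to faster growth on treatment.** With an assumed height SD of 4 to 6 cm, 1.14 SDS is 4.6 to 6.8 cm. At attained heights of 115 to 140 cm this adds between (140/135.44)^0.5 − 1 = 1.7% and (115/108.16)^1.0 − 1 = 6.3%. Most of the distortion is ordinary growth, not the response to treatment.

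**5. BMI.** For the child in step 2, BMI goes from 15/1.00² = 15.0 to 25/1.25² = 16.0 kg/m². That is +1.0 (7%), while weight rises by 67%. Dividing by height squared already removes most of the size effect. What remains is the normal change of BMI with age.

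**6. Standardised scale.** A child whose heart keeps its place for body size has an expected z-score change of 0, whatever the window.

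**The case against.** The strongest reply has four parts.

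- **These are descriptive measures.** They serve secondary objective 2, on patient characteristics. The safety objective rests on the event counts of Table 3. Section 10.5 names cardiac events as the events of special interest, and Table 9 records comorbidities at every visit. This stands. A reader might infer that the cardiac safety question goes unanswered; the protocol does not support that, because these other routes exist.
- **Most of the row is unaffected.** Ejection fraction and fractional shortening are ratios, the diastolic velocities are not lengths, and QTc, pulse rate and blood pressure have their own units. This also stands. It would be wrong to read the point as covering all cardiac endpoints.
- **BMI is not comparable.** A reader might infer that faster growth will look like weight gain. Step 5 does not show that, and weight SDS is in the same table. Only a minor point about age remains.
- **Nothing is lost by recording mm.** Z-scores could be derived later. That is true of the data, but the endpoint is fixed in mm, and choosing a reference after the results are known leaves the choice open.

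Describing results by treatment duration does not answer the concern. It makes the unequal windows visible, but growth still differs between the groups.

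**Conclusion.** The point holds for septal thickness and left ventricular end-diastolic diameter. As defined, their mean change is expected to rise by about 7% to 34% over 4 years from growth alone, and by more over longer windows. It cannot be separated from a cardiac effect in either direction. The size depends on the assumed start height, growth rate and scaling exponent. The direction does not, as long as the children grow and heart size follows body size.

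A reader might also infer that the best height responders will show much the largest increase. The expected treatment gain contributes only about 2% to 6% under the assumptions above, so this is the smaller part.

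No sample size and no primary analysis is affected. The change is worth making because it is cheap and because the protocol already standardises height, weight, IGF-1 and height velocity.

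**What to change.** In Table 4, define the two endpoints as change in z-score for body size, from one paediatric reference named in advance and using height and weight from the same visit. Keep the mm values as supportive description, and carry the definition into Table 10.

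As a minor addition in Table 6, report BMI SDS from a named national reference beside kg/m². Section 8.1.1.1 cites its growth reference for height only, so its coverage of BMI should be confirmed or another reference named.

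The cost is small. Table 9 schedules height and weight at every visit with an echocardiogram (baseline, M12, M24, M36, M48), so these are derived variables that need no new procedure. There are two drawbacks. A reference must be chosen and defended. Z-scores will also be missing wherever same-visit height or weight is missing, which Sections 8.2.8.2 and 8.4 lead one to expect in routine-care data.

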Change in complete blood count (CBC)	From start of Norditropin® treatment until end of follow-up	g/dL (Haemoglobin-Hb) G/L (White blood cells) G/L (Lymphocytes) G/L (Monocytes) G/L (Platelets)
Change in IGF-1 level	From start of Norditropin® treatment until end of follow-up	ng/ml and SDS
Change in HbA _{1c} level	From start of Norditropin® treatment until end of follow-up	%
Change in fasting insulin level	From start of Norditropin® treatment until end of follow-up	mg/dL or mUI/L
Change in fasting blood glucose level	From start of Norditropin® treatment until end of follow-up	mg/dL or g/L or mmol/L

Title of endpoint	Time frame	Unit
Change in fasting total cholesterol	From start of Norditropin® treatment until end of follow-up	mg/dl or g/L or mmol/L
Change in fasting triglycerides	From start of Norditropin® treatment until end of follow-up	mg/dL or g/L or mmol/L
Change in fasting HDL cholesterol	From start of Norditropin® treatment until end of follow-up	mg/dL or g/L or mmol/L
Change in fasting LDL cholesterol	From start of Norditropin® treatment until end of follow-up	mg/dL or g/L or mmol/L
Change in fasting total cholesterol/HDL ratio	From start of Norditropin® treatment until end of follow-up	NA
Change in inhibin B	From start of Norditropin® treatment until end of follow-up	pg/mL
Change in AMH	From start of Norditropin® treatment until end of follow-up	mg/mL
Change in LH (female from 8 years old and male from 9 years old)	From start of Norditropin® treatment until end of follow-up	mg/mL
Change in FSH (female from 8 years old and male from 9 years old)	From start of Norditropin® treatment until end of follow-up	UI/L or mUI/mL
Change in oestradiol (female from 8 years old and male from 9 years old))	From start of Norditropin® treatment until end of follow-up	pg/mL
Change in testosterone (female from 8 years old and male from 9 years old)	From start of Norditropin® treatment until end of follow-up	ng/mL

Secondary objective-3: To describe the therapeutic care of patients
 The endpoints related to the secondary objective-3 are listed in [Table 5](#).

Table 5 Secondary endpoints in relation to secondary objective 3

Title of endpoint	Time frame	Unit
Norditropin® treatment patterns		
Change in dose of Norditropin® treatment	From start of Norditropin® treatment until end of follow-up	mg/kg/day
Frequency of injections of Norditropin® treatment per week	From start of Norditropin® treatment until end of follow-up	Count of events

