8.7 Data analysis

8.7.1 Definition of analysis sets

The site populations will be defined as follows:

- Contacted sites: all reference and competence centres in France will be solicited to participate in this study
- Participating sites: all sites that agreed to participate in the study
- Active sites: all sites that included at least one eligible patient

The sites main characteristics (localisation, size) will be compared to ensure that the active sites are representative at the national level.

There are 3 patients population considered in this study:

- Overall population: all patients included in the eCRF,
- Full Analysis Set (FAS): all patients included in the eCRF and meeting all selection criteria. All secondary analyses will be performed on FAS.

- Growth Analysis Set (GAS): all patients from the FAS for which the primary criteria can be evaluated, i.e. height measurements available until the end of the 5-year follow-up or until NAH is reached, whatever occurs first.

The subgroups of interest for analyses are defined as follows:

- Norditropin[®] treatment duration: depending on age of onset and age at puberty onset, the patients may have shorter or longer time under GH treatment, which may highly influence auxological outcomes
- Mutated gene: PTPN11, SOC2, other

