8.7.2.2 Analysis of secondary endpoint(s)

All secondary endpoints will be described according to the outputs defined in the statistical methods.

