8.7.4 Sequential safety analysis/safety monitoring

All drug related adverse reactions (ADR), serious adverse drug reactions (SADR), serious adverse events (SAE) and adverse events (AE) will be classified and analysed from the initiation of the study drug until the end of follow-up.

Medical Dictionary for Regulatory Activities (MedDRA) version 19.1 or higher will be used for coding to "Lower Level Term (LLT)", "Preferred Term (PT)", "High Level Term (HLT)", "High Level Group Term (HLGT)" and the associated primary "System Organ Class (SOC)". CTCAE version 5 will be used to provide the grade.

AEs will be analysed as follows:

The number and percentage of patients experiencing:

- at least 1 on-treatment SAE/AE/SADR/ADR (including non-serious and serious irrespective of the relationship with the study treatment)
- at least 1 on-treatment SAE/AE/SADR/ADR related to the study treatment (including serious and non-serious AEs)
- at least 1 on-treatment serious SAE/SADR (regardless the relationship with the study treatment)
- at least 1 on-treatment serious SAE/SADR related to the study treatment
- at least 1 on-treatment SAE/AE/SADR/ADR leading to treatment discontinuation
- at least 1 on-treatment SAE/AE/SADR/ADR leading to treatment interruption/delay
- at least 1 on-treatment SAE/AE/SADR/ADR leading to dose decrease
- fatal on-treatment SAE/AE/SADR/ADR

They will be presented by SOC and preferred term.

Patient will be counted once by AE taking into account the maximum grade. The SOC/PT will be summarized (irrespective of the grade) and by maximum grade CTCAE (grade 1-2 ,3-4 and 5) as well. The incidence rate, corresponding to the number of patients experiencing at least one AE divided by the total person years of follow-up, will be calculated for each AE. A listing will be provided for fatal on-treatment AE. These analyses will be performed for the post-treatment AEs as well.

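### The window for change in HbA1c, fasting glucose, fasting insulin and IGF-1 can include time off Norditropin or on another GH, and only adverse events are separated by treatment status

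*Protocol*

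**What the plan says.** Table 4 in Protocol section 8.1.1.2 includes "Change in fasting blood glucose level", "Change in fasting insulin level", "Change in IGF-1 level" and the corresponding change in HbA1c. All four run from the start of Norditropin to the end of follow-up. They belong to secondary objective 2, clinical characteristics. The safety objective (Table 3) contains only event counts.

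For the analysis, section 8.7.1 states: "All secondary analyses will be performed on FAS". Section 8.7.2.2 adds: "All secondary endpoints will be described according to the outputs defined in the statistical methods". Those outputs (section 8.7.2) are general summary statistics, overall and by subgroup. They do not distinguish values on Norditropin from values off it.

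Adverse events are handled differently. Under section 8.7.4 they "will be classified and analysed from the initiation of the study drug until the end of follow-up", with tables restricted to on-treatment events, and then: "These analyses will be performed for the post-treatment AEs as well".

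**The concern.** The Transparency Committee's request, reported in sections 3 and 6.2, names the effect on glucose metabolism among the safety questions. HbA1c, fasting glucose and fasting insulin are the quantitative measures that bear on it most directly. IGF-1 is the marker that section 6.1 gives for monitoring tolerance when the dose is adjusted.

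If the end of follow-up falls after Norditropin has stopped, the last value describes a child off the drug. If the child has moved to another GH, it describes a different product. Table 10 lists safety among the reasons for a treatment modification and permanent stop among the types of modification. A child taken off Norditropin for a metabolic effect could therefore contribute later, possibly recovered, values to the description of that effect. The protocol makes the distinction for adverse events over the same window but not for these measurements.

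**Working it through.** The protocol gives no figure on this point, so there is none to reproduce. The check has three steps.

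**1. Can the window include time off Norditropin?** The relevant places, side by side:

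- Section 8.2.7: the reasons for leaving the study are opposition, loss to follow-up and death. Stopping Norditropin is not among them.
- Section 8.2.10 and Table 9: the end-of-treatment date, and the type, dose and start date of any GH given after Norditropin, are recorded during follow-up.
- Tables 5 and 10: permanent and temporary stops are recorded, and temporary stops are measured in months.
- Section 8.1: for children who had finished growing at inclusion, retrospective collection starts with Norditropin, and no end at treatment stop is stated.
- Section 8.7.4: post-treatment adverse events are to be tabulated, so post-treatment time is expected.

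The answer is yes. No rule in sections 8.7.1 to 8.7.2.2 then separates the values. The treatment-duration subgroup, introduced because "the patients may have shorter or longer time under GH treatment", sorts children by duration. One child's values on and off the drug stay together.

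**2. How many values are affected in a child who stops?** Table 9 schedules HbA1c, glucose and insulin after baseline at M12, M24, M36 and M48 (4 values). It schedules IGF-1 every six months from M6 to M48 (8 values). For an incident child who stops for good, or switches, and is followed to M48:

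| Stop just after | HbA1c, glucose, insulin off Norditropin | IGF-1 off Norditropin |
|---|---|---|
| M12 | 3/4 = 75% | 6/8 = 75% |
| M24 | 2/4 = 50% | 4/8 = 50% |
| M36 | 1/4 = 25% | 2/8 = 25% |

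These are counts of visits in a child who stops. They do not measure bias in the registry.

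**3. What could this do to the mean change at the end of follow-up?** Let f be the share of children off Norditropin at their last value, and r the share of the on-treatment change that persists at that point. If stoppers and non-stoppers had the same mean on-treatment change, then

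described change / on-treatment change = (1 − f) + f·r = 1 − f(1 − r).

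Neither f nor r is in the protocol. The values below are assumptions chosen to show the range:

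| f | r = 0 | r = 0.5 | r = 1 |
|---|---|---|---|
| 10% | 0.90 | 0.95 | 1.00 |
| 20% | 0.80 | 0.90 | 1.00 |
| 30% | 0.70 | 0.85 | 1.00 |
| 50% | 0.50 | 0.75 | 1.00 |

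For example, f = 20% and r = 0.5 give 1 − 0.20 × 0.5 = 0.90. The ratio is below 1 only when some children are off the drug (f > 0) and the change at least partly reverses (r < 1). If treatment stops only when follow-up ends, f = 0 and nothing is lost.

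**The case against.** The strongest reply is that this belongs in the statistical analysis plan. Table 3 gives adverse events the same window, and their split appears only at the analysis stage, so the Table 4 window is not wrong in itself. A separate plan is listed in Annex 1 and may add on-treatment tables. That possibility stands. However, section 8.7.2.3 expressly leaves the exploratory models to that plan, while section 8.7.2.2 leaves nothing to it and points to the protocol's own methods. The protocol chose to write the split down, and did so for adverse events alone.

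Section 8.1.1 describes all endpoints as assessed during routine use of Norditropin. This leans towards on-treatment assessment, but it sets no cut-off. It also covers the adverse events, which are analysed after treatment too, so it cannot mean on-treatment only.

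Adverse events give partial cover, and this also stands. Appendix A allows an abnormal laboratory finding to be an adverse event, and section 8.7.4 counts on-treatment events leading to discontinuation, interruption or dose decrease. A child stopped for a reported metabolic event is counted there whatever later values show. A shift in mean HbA1c or glucose that nobody reports as an event is not.

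A reader might go further and infer that the registry will understate the glucose effect. The documents do not support that. They do not say how many children stop, that Norditropin shifts these values at routine doses, or that a shift reverses on stopping. Children who switch remain on a GH, so their values need not look milder. Earlier on-treatment values also remain available for description.

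Finally, an analysis restricted to on-treatment visits has its own selection: children stopped for a metabolic effect disappear from later visits. This is correct and shapes the fix. Following every child to the end is a legitimate choice for a long-term registry, and that description should stay.

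**Conclusion.** The point holds as a limited one. Table 4, followed as written, allows values off Norditropin or on another GH to enter the described change in HbA1c, fasting glucose, fasting insulin and IGF-1. The protocol separates such time only for adverse events. The consequence is a description that can mix treatment states on a question the Transparency Committee named.

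The size is unknown and may be small or nil. Any softening of the effect rests on two assumptions absent from the protocol: that a relevant share of children stop before follow-up ends, and that the change reverses afterwards. For switchers the difficulty is attribution to the right product, not a milder effect. The change should be made because the distinction is cheap and the key dates are already collected, not because a bias has been shown.

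**What to change.** Keep the end-of-follow-up description and add the following to section 8.7.2.2 for the four measures:

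- Change from the start of Norditropin to the last on-treatment value, so that children who stopped early still contribute.
- Change at each scheduled visit (yearly; six-monthly for IGF-1) using on-treatment values, with the number of children still treated shown at each visit.
- A separate summary of values after the end of Norditropin, with values on another GH shown apart from values on no GH.
- A rule stating on which side values taken during a temporary stop fall.
- The number of children above the reference range (IGF-1 by SDS) at any on-treatment visit, only if the ranges are captured. Table 10 does not list them.

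The cost is a short addition to the text and a few extra tables. The values, end-of-treatment date, temporary stops and start of any later GH are already planned items, so no child needs another visit or test. One gap remains: a child who stops before the first yearly glucose measurement has no on-treatment post-baseline value for HbA1c, glucose or insulin. The number of such children should be reported.
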